6. RESEARCH PLAN

6.1 Selection of Subjects

6.1.1. Subject Population. Potential participants will be recruited from the STVHCS Polytrauma Rehabilitation Center (PRC), military medical treatment facilities, and from the local community. Recruitment will target veterans and active duty personnel having returned from a post-9/11 deployment with chronic PTHA and symptoms of posttraumatic stress.

6.1.2. Source of Research Material. Please find a description of these measures at the end of this protocol. Assessments will be administered in person whenever possible. However, in order to accommodate participant schedules and/or instances in which a participant may have left the local area at the time of a follow up assessment, we may collect full or partial assessments in person or via phone or electronic data capture using a secure link to the encrypted STRONG STAR database. Assessments completed via phone or remote electronic data capture will not include biospecimen collection. Reasonable efforts will be made to collect all data as described in this protocol, but we expect some participants may not be able to complete part or all of any given follow up assessment.

Randomized Clinical Trial of Cognitive-Behavior Therapy for Posttraumatic Headache

Assessments	PC/RA or IE	BL	TX	Post	3MFU	6MFU	DC
Demographics and Military Questionnaire	PC/RA	x					
History of Head Injuries and History of Head Injuries Addendum	PC/RA	x		x	x	x	
Deployment Risk and Resiliency Inventory_2_Deployment Environment (DRRI_2_D)	PC/RA	x					
Deployment Risk and Resiliency Inventory_2_Postbattle Experiences (DRRI_2_P)	PC/RA	x					
Deployment Risk and Resiliency Inventory_2_Combat Experiences (DRRI_2_C)	PC/RA	x					
Life Events Checklist-5 (LEC-5)	PC/RA	x		x	x	x	
Patient Health Questionnaire-9 (PHQ-9)	PC/RA	x	x	x	x	x	
Depressive Symptom Index –Suicide Subscale (DSI-SS)	PC/RA	x		x	x	x	
Generalized Anxiety Disorder-7 (GAD-7)	PC/RA	x		x	x	x	
Alcohol Use Disorders Identification Test –Self Report (AUDIT)	PC/RA	x					
Quick Drinking Screen (QDS)	PC/RA	x		x	x	x	
Fagerstrom Test for Nicotine Dependence (FTND)	Self-report	x		x	x	x	
Fagerstrom Test for Nicotine Dependence-Smokeless Tobacco (FTND-ST)	Self-report	x		x	x	x	
Headache Management Self-efficacy Scale (HMSE)	PC/RA	x		x	x	x	
Headache-Specific Locus of Control Scale (HSLC)	PC/RA	x		x	x	x	
Headache Impact Test (HIT-6)	PC/RA	x		x	x	x	x
Neurobehavioral Symptom Inventory (NSI)	PC/RA	x		x	x	x	

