Credibility and Expectancy Questionnaire (CEQ)	PC/RA		x	x			
Pre-Treatment Health Interview (+ BL PTHA addendum)	IE	x					
Post-Treatment Health Interview (+ FU PTHA addendum)	IE			x	x	x	
Structured Diagnostic Interview for Headache –Revised (SDIH-R)	IE	x		x	x	x	
Ohio State University TBI Identification Method-Interview Form (OSU TBI-ID-SF)	IE	x					
Selection of Index Event for the CAPS-5	IE	x					
Clinician Administered PTSD Scale-5 (CAPS-5)	IE	x		x	x	x	
Self-Injurious Thoughts and Behaviors Interview –Short Form	IE	x		x	x	x	
Tinnitus Functional Index	IE	x		x	x	x	
PTSD Checklist List-5 (PCL-5)	PC/RA	x	x	x	x	x	x
Cognitive Emotions Regulations Questionnaire –Short (CERQ-Short)	PC/RA	x		x	x	x	
Posttraumatic Cognitions Inventory (PTCI)	PC/RA	x		x	x	x	
Response to Stressful Experiences Scale (RSES)	PC/RA	x					
Patient Health Questionnaire-15 (PHQ-15)	PC/RA	x		x	x	x	
Veterans Rand 12 Item Health Survey (VR-12)	PC/RA	x		x	x	x	
PROMIS Sexual Function	PC/RA	x		x	x	x	
Brief-Inventory of Psychosocial Functioning (B-IPF)	PC/RA	x		x	x	x	
Insomnia Severity Index (ISI)	PC/RA	x		x	x	x	
PROMIS Sleep-Related Impairment and Disturbance	PC/RA	x		x	x	x	

Assessments (cont.)	PC/RA or IE	BL	TX	Post	3MFU	6MFU	DC
Snoring, Tired, Observed, Blood Pressure (STOP)	PC/R A	X					
Community Reintegration of Injured Service Members (CRIS)	PC/R A	X		X	X	X	
NIH Cognition Battery (via computer)	PC/R A	X		X	X	X	
PTHA Study Missing Data Assessment	PC/R A						X
Online Forms:	1.) Daily Headache Diary 2.) Profile of Mood States 3.) Sleep Quality/Quantity 4.) Daily Stress Inventory						
					Participant will complete online entries twice daily. Entries will occur before, during, and after treatment for a total of 14 weeks.		

* DC = participant discontinued participation (i.e., drop out of treatment or follow-up)

6.1.3. Inclusion and Exclusion Criteria.

Inclusion Criteria:

- adult (ages 18 and above)
- U.S. military Veterans and active duty personnel with military service during a post-9/11 deployment
- have sustained a traumatic head injury.

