- Cognitive Processing Therapy-Cognitive Only (CPT-C). Cognitive Processing Therapy (CPT) is a trauma-focused treatment that involves learning to recognize and challenge thoughts related to traumatic brain injury. Participants assigned to this treatment arm will be asked to meet with a study therapist twice a week for

Randomized Clinical Trial of Cognitive-Behavior Therapy for Posttraumatic Headache

approximately 6-weeks for a total of 12 one-hour sessions. Each treatment will take place at the South Texas Veterans Healthcare System (Audie Murphy Hospital) or the UTHSCSA STRONG STAR clinic. During this treatment, participants will be asked to think about how they received their traumatic brain injury and their beliefs about the meaning of the event, as well as their current beliefs about themselves and others. Topics such as safety, trust, control, self-esteem, and intimacy will be discussed. Participants will be expected to complete assignments outside of session to practice skills learned in treatment.

- Treatment as Usual (TAU). Participants assigned into the Treatment as Usual (TAU) condition will receive treatment by their primary provider as indicated. The participants will meet with study staff twice during the treatment phase to complete assessments.

Assessments

- All participants regardless of treatment group will be asked to complete headache diary on-line twice a day.
- Blood will be drawn prior to treatment, during two of the treatment sessions, and at the 1- and 6-month assessments.
- Two weeks before the scheduled 1-, 3- and 6-month assessments, participants will once again be asked to complete headache diaries for two weeks prior to the evaluations.

All evaluations will be audio-recorded and CCBT and CPT-C therapy sessions will be audio-recorded to make sure that the study staff is correctly following the study procedures. These recordings will be reviewed by research experts who are part of the research team.

Assessment of Discontinued (i.e., treatment/assessment dropout) participants.

- All participants who discontinued participation in this study before completing study treatment and follow-up assessments will be contacted by phone by a project coordinator or research assistant and asked about their willingness to participate in a 10-15 assessment of their symptoms and reason for discontinuing participation. Participants will have the option to opt in to the assessment by giving verbal consent over the phone.

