Advanced Data Center (ADC) has 24x7 onsite security, card key, biometric access controls and video surveillance. University of Texas Health Science Center at San Antonio (UTHSCSA) ADC facility also maintains Gen 2 firewall devices to protect and prohibit any unauthorized access to UTHSCSA data. All UTHSCSA network devices are monitored by state of the art monitoring applications that include configuration audit, management, and availability 24x7.

Statistical Consideration

6.3.1 Sample Size Estimation.

This study will consent approximately 438 study participants with the goal of having 192 participants randomized for analysis.

6.3.2 Primary (i.e., primary outcome variables) and secondary endpoints.

The primary outcomes are headache symptoms and PTSD symptoms.

6.3.3 Data analysis.

Treatment groups will be compared on baseline variables. Dropout during treatment resulting in lack of outcome data can bias analyses. If attrition can be successfully modeled with logistic regression on the basis of baseline characteristics, and particularly if there is evidence of differential attrition, strategies such as inverse probability weighting can supplement the outcome analyses. Assuming that headache disability data (HIT-6; our primary outcome for this research) is reasonably normally distributed across the sample, treatment effects of the clinical interventions (CCBT and CPT-C) over the Treatment as Usual- Control condition will be analyzed using a general linear mixed (GLM) model with baseline scores used as a covariate. Unlike ANOVA, mixed effects models permit heterogeneity of variance in the treatment groups. If HIT-6 data are non-normal, a generalized linear model will be used (e.g., Poisson regression).

Two joint primary comparisons will be conducted comparing both active treatments to TAU. To adjust the alpha level for these joint hypotheses, we will interpret both at the alpha = 0.025 significance level. Secondary analyses will examine differences between the two active interventions as well as sensitivity analyses of the primary outcomes considering missing data, adherence to the protocol, or imbalances between the groups at baseline. Additional analyses will consider the secondary outcomes and differences between the groups at other time points.

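### The primary outcome, HIT-6, is not measured during treatment, so the primary model cannot use early HIT-6 response for anyone who misses the post-treatment assessment

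*Combined protocol and SAP*

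**What the plan says.** Section 6.3.3 identifies the primary endpoint as "headache disability data (HIT-6; our primary outcome for this research") and analyses it with a mixed model that has baseline as a covariate. The same section states that "Dropout during treatment resulting in lack of outcome data can bias analyses". Its named remedy is inverse probability weighting, as a supplement, if attrition can be modelled from baseline characteristics. It also mentions sensitivity analyses for missing data, without a method.

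In the assessment table of section 6.1.2, the row "Headache Impact Test (HIT-6") is marked at baseline, Post, 3 months, 6 months and discontinuation (DC), and is blank under TX. The rows "Patient Health Questionnaire-9 (PHQ-9") and "PTSD Checklist List-5 (PCL-5") both carry a TX mark.

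Treatment-phase contacts exist in every arm. Therapy participants attend sessions, and for TAU section 6.2 says: "The participants will meet with study staff twice during the treatment phase to complete assessments". All participants have two blood draws in that phase.

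For dropouts, the table footnote reads "DC = participant discontinued participation (i.e., drop out of treatment or follow-up"), and section 6.2 says that "All participants who discontinued participation in this study before completing study treatment and follow-up assessments will be contacted by phone". That call includes HIT-6 and PCL-5. It needs verbal opt-in, and section 6.1.7 says it is unpaid.

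**The concern.** Dropout from a talking therapy may well depend on how headaches go in the first weeks. If participants without early relief leave more often, those still observed in a therapy arm look better than everyone randomized to it, and the comparison with TAU is tilted towards therapy. A mixed model can allow for such dropout only through outcome values seen before the participant left. Here the only HIT-6 value scheduled before Post is the baseline. The plan takes PTSD and depression scores during treatment but not the headache score on which the primary comparisons rest. Both primary comparisons, each therapy against TAU, are exposed.

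**Working it through.** **1. The table rows side by side (section 6.1.2)**

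| Measure | BL | TX | Post | 3 months | 6 months | DC |
|---|---|---|---|---|---|---|
| HIT-6 (primary) | x | – | x | x | x | x |
| PCL-5 | x | x | x | x | x | x |
| PHQ-9 | x | x | x | x | x | – |

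**2. Who has no post-baseline HIT-6.** A participant must stop treatment, miss Post, 3 months and 6 months (section 6.1.2 allows phone or electronic collection), and not give a HIT-6 at the discontinuation call. Anyone who does give one at that call has a value, but the plan does not say when it is taken, which visit it stands for, or whether it enters the primary model.

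**3. What the planned methods can use.** With baseline as covariate and no TX value, the model has no early HIT-6 response for anyone who misses Post. Weights built from baseline variables cannot reflect what happens after baseline.

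**4. Size.** The documents give no dropout rate and no bias figure, so there is no planned value to reproduce. The power statement is a separate matter and is used only for scale.

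Inputs from section 6.3.3: 64 per arm; SD = 2.8/0.52 = 5.38; baseline–endpoint correlation 0.50. Assumptions: correlation baseline–mid-treatment 0.6 and mid-treatment–post 0.7; TAU loss 10% at random; therapy-arm loss about 28–33%, with log-odds of dropout rising by 0.5, 1.0 or 1.5 per SD of worse early change.

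Closed form. At a given baseline, the slope of the post score on the mid-treatment score is

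(0.7 − 0.6 × 0.5) / (1 − 0.6²) = 0.40/0.64 = 0.625.

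If a fraction f of the therapy arm is lost, and those lost are Δ points worse at mid-treatment than those kept, the bias is about 0.625 × f × Δ. With f = 0.30 this is 0.1875Δ.

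- Simulated bias with no dropout recovered: about 0.3, 0.6 and 0.9 points for the three strengths of dependence, in favour of therapy, whether the true difference is 0 or 2.8. In the closed form, 0.3 to 0.9 corresponds to Δ = 0.3/0.1875 = 1.6 up to 0.9/0.1875 = 4.8 points.
- A random half of dropouts gives a later HIT-6 that is used as an endpoint value. Measured from the whole arm's mean, completers stand at −0.30Δ and dropouts at +0.70Δ, so the bias has size 0.625 × (0.70 × 0.30 − 0.15 × 0.70)/0.85 × Δ = 0.077Δ, or 0.12 to 0.37. Simulation gives about 0.15 to 0.37.
- 15% therapy-arm loss with half recovered: simulated bias 0.11 to 0.17.
- A mid-treatment HIT-6 obtained from everyone before dropout and used in the model: simulated bias 0.02 or less.
- The same addition when half of the dropouts leave before that contact: about 0.1 to 0.4 remains.

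Against the 2.8-point target, 0.3 to 0.9 is 11% to 32%, and 0.15 to 0.4 is 5% to 14%. If 5.38 is the SD after baseline adjustment, the raw SD is 5.38/√0.75 = 6.22, and each bias grows by a factor of 6.22/5.38 = 1.16.

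**The case against.** A reader might infer that everyone who drops out during treatment has no scheduled HIT-6 and is lost to the primary analysis. The documents do not support that. The HIT-6 row carries a DC mark, section 6.2 has all discontinued participants phoned and offered the HIT-6, and nothing cancels the Post, 3- or 6-month assessments for someone who only stops sessions. Those follow-ups can be done remotely.

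The plan also has other information on dropouts. The online headache diary is completed twice daily before, during and after treatment, 14 weeks in all, so early headache course is recorded in every arm. A short Missing Data Assessment is meant to help judge the missingness and support imputation. Weighting is given as one example of a strategy. Measuring disability before and after treatment, with diaries between, is a legitimate design.

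Finally, the size rests on assumed differential dropout, and a near-zero bias after the change is built into a simulation in which everyone reaches the mid-treatment contact.

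Most of this stands and limits the point. It does not remove it. The call is voluntary and unpaid, and its HIT-6 has no stated place in the analysis. The imputation purpose is stated for the five-item Missing Data Assessment, not for the HIT-6 given at the call. The diary measures headache days, frequency, duration and intensity rather than HIT-6 disability, and section 6.3.3 gives it no role in the HIT-6 model.

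**Conclusion.** The point holds in a limited form. The primary outcome has no treatment-phase measurement although two other scales do, and baseline weighting cannot make up for dropout that follows early headache course. The affected participants are those who miss the later assessments, and most of all those who also give no HIT-6 at the discontinuation call.

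The size is conditional on assumed dropout: about 0.3 to 0.9 HIT-6 points in favour of therapy if no dropout is recovered, about 0.15 to 0.4 if half give a usable later value, and less if dropout is milder or similar across arms. The upper figures are near worst case and should not be read as an expected bias. The remedy works only for participants who reach a treatment-phase HIT-6. This is an optional, low-cost improvement; the documents do not contradict themselves here.

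**What to change.** - Mark HIT-6 under TX in the section 6.1.2 table. Give it at the two treatment-phase contacts in TAU and at matching therapy sessions, for example the two with a blood draw.
- In section 6.3.3, enter these values as repeated outcomes with arm-by-visit terms, leaving the primary contrast as it is.
- Name the on-treatment diary measures as auxiliary variables in the missing-data analyses (imputation or weighting).
- State when the discontinuation HIT-6 is taken, which visit it maps to, and whether it enters the primary model or only sensitivity analyses.

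The cost is six extra self-report items at two contacts that already take place, one table change and a few lines in section 6.3.3. There is no new visit. The drawbacks are slightly more burden and missing values for participants already past treatment. Early leavers would still be missed, so the diary and discontinuation rules are worth adding even if the TX measurement is not.

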- Those who agree to participate will be asked questions about global change in headache and PTSD symptoms, their perceptions of study participation and study treatments, their reason(s) for discontinuing participation in the study, and verbal administration of the HIT-6 and PCL-5 to assess headache and PTSD symptom severity.

6.2.1 Collection of Human Biological Specimens.

All participants will have blood drawn prior to treatment, at two treatment sessions, and 1- and 6-months (following treatment completion) coordinated through the CAP Biomarkers and Genomics Core. A skilled phlebotomist will draw the samples. All blood samples will be collected at the Audie L. Murphy VA Hospital or the UTHSCSA STRONG STAR clinic.

6.2.1.1 Laboratory evaluations and special precautions.

All blood samples will be collected at the Audie L. Murphy VA Hospital or the UTHSCSA STRONG STAR clinic and then transported to the CAP Biomarkers and Genomics Core in the UTHSCSA Department of Psychiatry and Behavioral Sciences at the UT Health-Long School of Medicine in room 727F for processing and storage. This location is monitored 24-7 by a wireless monitoring system on the Isensix system and has approval by the STVHCS and Central VA office as a VA-Approved Tissue Bank. The study staff will be available to offer assistance if the participant is distressed at any point during any procedures.

6.2.1.2 Specimen storage.

Biological specimens will be coded with a digital bar code that can be linked to the study and subject only by key-codes maintained by the CAP Data Management and Biostatistics Core.

6.2.2 Data Collection.

Hardcopies of data will be stored in locked file cabinets within a dedicated, cipher/keyed room at the Audie L. Murphy VA Hospital in the Polytrauma Rehabilitation Center or the UTHSCSA STRONG STAR clinic (iaw local Privacy policies).

Electronic data will be stored on a FISMA compliant, secure, research database at UTHSCSA, <https://delta.uthscsa.edu/ssdashboard/login.aspx>. The STRONG STAR data server is physically located at the

Randomized Clinical Trial of Cognitive-Behavior Therapy for Posttraumatic Headache

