A recent study helped to guide our determination of what constitutes a clinically meaningful change in perceived headache disability and the proposed study was powered in light of these differences. In the primary care setting, HIT-6 changes ranging from 2.5 (95% CI: -3.3 to -1.7) were perceived as "somewhat better" and changes up to 5.9 (95% CI: -7.6 to -4.1) were perceived as "much better." We considered a meaningful change as somewhere between these two global impressions and used this marker as an index of clinically significant between-group differences. Our study is powered to detect an effect size of 2.8 points between groups after controlling for baseline scores (i.e., a residualized change) and constitutes an effect that would be meaningful to most headache sufferers. Assuming an alpha level of 0.025, group sample sizes of $n = 64$ ($N = 192$), and a moderate correlation between the baseline scores and final endpoints ($r = 0.50$), we will have power = 0.80 to detect an effect size of $d = 0.52$ between both of the joint primary comparisons. In realistic terms, this will allow us to detect a change of 2.8 points on the HIT-6 between the active treatment and the controls. Changes smaller than this magnitude are unlikely to be clinically meaningful.

6.4 Confidentiality.

Confidentiality will be safeguarded through a number of Consortium controls already in place for existing studies. First, all assessments will occur in a private room. Completed hard-copy assessments will be stored in a file in a locked drawer that is located in a locked office at the VA or the UTHSCSA STRONG STAR clinic. Patient identifiers are removed from all charts and associated only with a number identifier. Data will be transcribed into the Consortium database by the study coordinator or a trained research assistant using a double-entry method. All digital research data files will be encrypted and password-protected on the UT Health Science Center's FISMA-compliant network, with files accessible only to the Consortium Data Core. All UTHSCSA STRONG STAR network connectivity is segmented with Access Control Lists and is not accessible to any other UTHSCSA network segments. The STRONG STAR data server is physically located at the Advanced Data Center (ADC) has 24x7 onsite

Randomized Clinical Trial of Cognitive-Behavior Therapy for Posttraumatic Headache

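### Section 6.3.2 makes PTSD symptoms a primary outcome, but the model, alpha split and power in 6.3.3 cover only HIT-6

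*Combined protocol and SAP*

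**What the plan says.** Section 6.3.2, whose heading covers primary and secondary endpoints, consists of one sentence: "The primary outcomes are headache symptoms and PTSD symptoms". It names no instrument and lists no secondary endpoint.

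Section 6.3.3 introduces its model with "headache disability data (HIT-6; our primary outcome for this research", in the singular, and describes the mixed model for that scale only. It continues: "Two joint primary comparisons will be conducted comparing both active treatments to TAU". On error control it says: "To adjust the alpha level for these joint hypotheses, we will interpret both at the alpha = 0.025 significance level". The power paragraph assumes 64 per group (192 in all), a baseline-to-endpoint correlation of 0.50, power of 0.80 and d = 0.52, and concludes that "this will allow us to detect a change of 2.8 points on the HIT-6 between the active treatment and the controls". It gives no effect size, SD or power for PTSD.

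Two other phrases in 6.3.3 bear on PTSD's status without settling it. One plans "sensitivity analyses of the primary outcomes considering missing data", with outcomes in the plural. The other reads "Additional analyses will consider the secondary outcomes and differences between the groups at other time points", but the secondary outcomes are not listed.

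Two PTSD severity measures could serve. In the assessment table (6.1.2), CAPS-5 and PCL-5 are both scheduled at baseline, post-treatment, 3 months and 6 months. For participants who discontinue, 6.2 specifies "verbal administration of the HIT-6 and PCL-5 to assess headache and PTSD symptom severity". CAPS-5 is not given at that contact.

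**The concern.** What counts as a primary success decides what the trial may claim. Under 6.3.3, a PTSD result is secondary by implication. Under 6.3.2, the same result could be reported as a primary success, on whichever of the two scales is chosen. A report could cite this protocol for either position.

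The alpha split and the power were built for two HIT-6 comparisons, and those use all of 0.05. If PTSD is also primary, neither the error control nor the power covers the primary outcomes as listed. With no success rule, a reader cannot tell whether error would rise (either outcome suffices) or power would fall (both are needed).

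The scale is more than a label. Only PCL-5 is collected from participants who drop out, so the choice also changes how much data is missing.

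**Working it through.** **Inputs from the protocol (6.3.3):** n = 64 per arm, three arms, alpha 0.025 per comparison, r = 0.50, d = 0.52, power 0.80.

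**Assumptions not in the documents:** two-sided tests, no dropout, a range of correlations between HIT-6 and the PTSD measure, and, for the both-outcomes rule, a PTSD effect and baseline correlation equal to those for HIT-6.

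**Step 1. Reproduce the stated power.** Take d = 0.52 on the raw SD. Adjusting for baseline leaves a residual SD factor of sqrt(1 - 0.50²) = 0.866, so the effective d is 0.52/0.866 = 0.600. The expected z is 0.600 × sqrt(64/2) = 3.40, and the critical value at two-sided 0.025 is 2.2414.
- One comparison: Φ(3.40 - 2.24) = 0.876.
- Both comparisons, whose test statistics correlate at 0.5 through the shared TAU arm: 0.796 (0.789 with a t-based simulation).

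The second figure matches the stated 0.80. The plan's power is thus the power to win both HIT-6 comparisons, obtained from HIT-6 inputs alone. If d = 0.52 is instead put on the residual SD, the results are 0.758 for one comparison and 0.631 for both, and neither reproduces 0.80.

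**Step 2. Error for the tests that are written down.** The bound is 2 × 0.025 = 0.05. With the 0.5 correlation, family-wise error is 4.65%. Nothing is left over for PTSD.

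**Step 3. Error if PTSD were also tested at 0.025 per arm and either outcome counted.** The bound is 4 × 0.025 = 0.10. The four-test correlation matrix combines 0.5 between arms with an assumed correlation between outcomes:

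| Outcome correlation | 0 | 0.3 | 0.5 | 0.7 | 0.9 |
|---|---|---|---|---|---|
| Family-wise error | 9.1% | 8.9% | 8.5% | 7.9% | 6.6% |

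**Step 4. Cost of controlling Step 3.** Dividing 0.05 over four tests gives 0.0125 each. HIT-6 power at 64 per arm becomes 0.816 for one comparison (from 0.876) and 0.709 for both (from 0.796). Holm's procedure rejects whatever this equal split rejects, so these are lower bounds for Holm.

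**Step 5. Both outcomes required within an arm, each at 0.025.** A false claim in an arm needs a significant result on an outcome with no true effect, so the bound over two arms is again 2 × 0.025 = 0.05. Simulation gives 0.1% to 2.6% when no outcome has an effect, and at most 4.9% in the other configurations checked. Per-arm power falls from 0.876 to 0.77 at outcome correlation 0 (0.876² = 0.767), rising to 0.84 at 0.9.

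**The case against.** The strongest reply is that 6.3.3 is the operative text. It names the instrument, the model, the comparisons, the alpha and the power, while 6.3.2 is a single line naming symptom domains. The alpha sentence does not mention HIT-6, but the count of two, the HIT-6 model before it and the HIT-6 power after it all indicate that it covers HIT-6 only. On that reading PTSD is secondary and 6.3.2 is an unreconciled summary line.

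Part of this stands: the HIT-6 comparisons are confirmatory and their error is controlled. It does not settle PTSD. Section 6.3.2 is where endpoints are defined, 6.3.3 itself uses the plural for primary outcomes, and PTSD is nowhere listed as secondary. The abstract aims at relief of both headache and posttraumatic stress symptoms, and the background section explains that CPT-C was added as a PTSD treatment arm. No passage says which section governs.

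Two stronger readings are tempting and are not supported.
- A reader might infer that the plan runs at a family-wise error near 9% or 10%. No passage plans PTSD tests at 0.025 or an either-outcome rule, and the only tests written down stay below 5%.
- A reader might put d = 0.52 on the residual SD, since the protocol speaks of residualized change. That would give per-comparison power of 0.67 after an alpha split, or per-arm power of 0.58 to 0.70 if both outcomes must win. That reading does not reproduce the stated 0.80, so those figures should not be used.

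The visit at which the primary outcome is judged is not named for HIT-6 either. That is a separate matter and adds no weight here.

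**Conclusion.** The contradiction is real and the documents do not resolve it. PTSD's status is not missing: 6.3.2 calls it primary, and 6.3.3 proceeds as if HIT-6 alone were. What is missing, if 6.3.2 stands, is the PTSD scale, the success rule, the alpha and the power.

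The size depends on the role PTSD is given:
- Secondary: stated alpha (4.65%, bound 5%) and stated power (0.796) are unaffected.
- Primary, either outcome counts, all tests at 0.025: family-wise error 6.6% to 9.1%.
- Primary, either outcome counts, alpha split to 0.0125: joint HIT-6 power about 0.71, or 0.82 per comparison.
- Primary, both outcomes needed: no inflation, per-arm power 0.77 to 0.84 instead of 0.88.

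These figures rest on the assumptions listed with the working. The contradiction itself rests on none of them. It must be fixed, because the choice cannot credibly be made once results by arm are known.

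**What to change.** Reconcile 6.3.2 with 6.3.3 before results by arm are examined. The documents do not give the state of the data. If results have already been examined, state the change and when it was made. Which option to take is a decision about objectives and belongs to the sponsor.

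(a) Make HIT-6 the single primary outcome, keep the two comparisons at 0.025, and list PTSD severity on one named scale (CAPS-5 or PCL-5) as secondary, with the other secondary outcomes listed too. This is a text change that leaves the stated alpha and power as they are. The cost is that a PTSD benefit can no longer be a primary claim, which matters given the dual aim and the CPT-C arm.

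(b) Keep both outcomes primary. Name the PTSD scale, state whether success needs either outcome or both, control error over all four tests if either counts (for example by Holm), and restate the power for that rule at the planned 64 per arm. This needs no more participants, but it costs power under either rule, by the amounts given in the verdict.

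Under either option, the text should say how the choice of scale fits with PCL-5 being the only PTSD measure taken from participants who discontinue.
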